3.2. Schedule of Events

Schedule of events can be found in Section 1.3 of the protocol.

3.3. Changes to Protocol Defined Analyses

No changes.

4. PLANNED ANALYSES

- There will be no Data Monitoring Committee (DMC) meetings for this study.

4.1. Interim Analysis

There will be no interim analyses for this study.

4.2. First Analysis

A First Analysis will be performed on all immunogenicity, reactogenicity and safety data available and as clean as possible, when data for at least primary and secondary endpoints up to Visit 2 (Day 31) (Co-Ad group) or Visit 3 (Day 61) (Control group) are available for all participants. This analysis will be considered as final for those endpoints.

4.3. EOS Analysis

An End of Study analysis will include all data obtained until 6 months post-last dose.

If for any reason the First Analysis could not be performed prior to the EOS Analysis, then the First Analysis will be performed at EOS analysis.

5. ANALYSIS SETS

Agreement and authorization of participants included / excluded from each analysis set will be conducted prior to

production for the interim analysis.

5.1. Process for Analysis Set Assignment

- Definitions for analysis sets are provided below.
- Prior to database lock, a transfer of raw data from the electronic Case Report Form (eCRF) will occur, and participants will be assigned to analysis sets in accordance with the definitions in this SAP and the available data at that time. However, the protocol deviations will be monitored continuously throughout the study.
- Listings presenting participants excluded from each final analysis set and reasons for exclusion will be prepared for sponsor review ahead of database lock in order to allow appropriate related data queries to be issued.
- A Data Review meeting will be held to confirm analysis set assignment, along with protocol deviations review (see protocol deviations management plan [PDMP], to include details of which PDs lead to exclusion from per protocol analyses), for each participant and any changes will be recorded. Changes will be implemented, and an updated analysis set assignment will be approved by the sponsor. The Data Review Plan will be shared with the sponsor for review prior to the Data Review meeting.
- Sponsor authorization of the analysis sets will be necessary prior to database lock. Once approved, analysis sets will be finalized, and the database will be locked.
- After database lock, the final analysis sets will be derived using the final study data, i.e., clinical database (eCRF), eDiary, external vendor data (immunogenicity results) and protocol deviations log.

5.2. Screened Set [SCR]

- All participants who were screened for eligibility.

5.3. Enrolled Set [ENR]

All participants in the SCR who were randomized or received study intervention or have undergone an invasive procedure. For analyses and displays based on ENR, participants will be classified according to randomized intervention.

5.4. Exposed Set [ES]

All participants in the ENR who received a study intervention. Analysis per group is based on the study intervention administered (i.e., study intervention actually received).

5.5. Per Protocol Set [PPS]

RSV PPS:

All eligible participants in the ES:

- who received RSV vaccine as per protocol in the control group and received both study interventions in the Co-Ad group
- who had immunogenicity results pre- and post-dose for RSV neutralizing titers
- who complied with blood draw interval for RSV samples
- without intercurrent medical conditions* that may interfere with immunogenicity and without prohibited concomitant medication / vaccination up to blood sample post RSV vaccination for control group and Co-Ad group,
- who do not meet any of the criteria for elimination up to blood sample post RSV vaccination for control group and Co-Ad group (i.e., control group participants need to meet all above criteria at Visits 2 and 3; Co-Ad group participants need to meet all above criteria at Visits 1 and 2).

PCV PPS:

All eligible participants in the ES:

- who received PCV vaccine as per protocol in the control group and received both study interventions in the Co-Ad group
- who had immunogenicity results pre- and post-dose for opsonophagocytic antibodies (OP Ab) titers
- who complied with blood draw interval for PCV20 samples
- without intercurrent medical conditions that may interfere with immunogenicity and without prohibited concomitant medication / vaccination* up to blood sample post PCV20 vaccination for control group and Co-Ad group, and
- who do not meet any of the criteria for elimination up to blood sample post RSV vaccination for control group and Co-Ad group (i.e., control group and Co-Ad group participants need to meet all above criteria at Visits 1 and 2)

*Intercurrent medical conditions that may lead to elimination from the PPS are defined as confirmed immunodeficiency condition, use of prohibited medication, or development of RSV or pneumococcal disease in the interval between study intervention administration and the collection of blood specimen for immunogenicity (i.e., Day 31 for Co-Ad group for PCV20 intervention; Day 31 for Co-Ad group and Day 61 for Control group for RSVPreF3 OA intervention).

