^a Visit 3 should preferably be done on site but if deemed necessary (during special circumstances such as the COVID-19 pandemic), this study visit can be replaced by a home visit conducted by authorized staff. Any information from the participant required according to study procedures and not collected during the home visit can be obtained by means of a phone call conducted by the site staff.

^b Six months after last vaccination. For this contact, multiple formats (e.g., email, text message, fax, or phone call) can be proposed by the study site.

^c Visit window shown in [Table 4](#)

^d Sample collected at Day 1 will be used as baseline for PCV20 antibody titers.

^e Sample collected at Day 31 will be used for the post-vaccination PCV20 vaccine-related testing. This sample will also be used as baseline for the RSV vaccination in the Control group.

^f Sample collected at Day 61 will be used for the post-vaccination RSV vaccine-related testing.

^g The route for measuring body temperature can be oral or axillary. Fever is defined as temperature $\geq 38.0^{\circ}\text{C}/100.4^{\circ}\text{F}$, regardless of the location of measurement.

^h Designated site staff should review the eDiary frequently during the active event collection period to assess participant/caregiver compliance and monitor reported events.

ⁱ SAEs related to study participation, or to a concurrent GSK medication/vaccine should be collected from the time of consent obtained (prior to study vaccine administration) up to EoS.

Table 3 Interval Between Study Visits (Co-ad Group)

Interval	Planned visit interval	Allowed interval (Visit window)
Visit 1 (Day 1/study intervention administration) → Visit 2 (Day 31)	30 days	30-42 days
Visit 1 → phone contact	180 days	180-210 days

Table 4 Interval Between Study Visits (Control Group)

Interval	Planned visit interval	Allowed interval (Visit window)
Visit 1 (Day 1/study intervention administration) → Visit 2 (Day 31)	30 days	30-42 days
Visit 2 (Day 31/study intervention administration) → Visit 3 (Day 61)	30 days	30-42 days
Visit 2 → phone contact	180 days	180-210 days

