2.3. Statistical Hypotheses

The study includes the following confirmatory primary objectives.

- To demonstrate the non-inferiority of PCV20 when co-administered with the RSVPreF3 OA investigational vaccine compared to PCV20 administered alone in terms of OP Ab titers GMT ratio for each of the pneumococcal vaccine serotypes (ST) at 1 month after the PCV20 vaccine (i.e., at Day 31 [Visit 2] for both study intervention groups).

Null hypothesis vs. Alternative hypothesis:

$$H_0: \mu_{Control\ group} - \mu_{Co-Ad\ group} > \log(2) \text{ vs. } H_a: \mu_{Control\ group} - \mu_{Co-Ad\ group} \leq \log(2)$$

where μ represents the estimated mean of log transformed antibody titers at 1 month after the PCV20 vaccine dose. The null hypothesis will be rejected if the upper limit of the two-sided 95% CI for the group GMT ratio (Control group divided by Co-Ad group) in antibody titers for each of the pneumococcal vaccine STs 1 month after the PCV20 vaccine ≤ 2

- To demonstrate the non-inferiority of RSVPreF3 OA investigational vaccine when co-administered with the PCV20 vaccine compared to RSVPreF3 OA investigational vaccine administered alone in terms of RSV-A neutralization antibody GMT ratio at 1 month after the RSVPreF3 OA investigational vaccine dose (i.e., at Day 31 [Visit 2] for the Co-Ad group and at Day 61 [Visit 3] for the Control group).

Null hypothesis vs. Alternative hypothesis:

$$H_0: \mu_{Control\ group} - \mu_{Co-Ad\ group} > \log(1.5) \text{ vs. } H_a: \mu_{Control\ group} - \mu_{Co-Ad\ group} \leq \log(1.5)$$

where μ represents the estimated mean of log transformed RSV-A neutralization antibody titers at 1 month after the RSVPreF3 OA investigational vaccine dose. The null hypothesis will be rejected if the upper limit of the two-sided 95% confidence interval (CI) for the study intervention group GMT ratio (Control group divided by Co-Ad group) in RSV-A neutralization antibody titers 1 month after the RSVPreF3 IA investigational vaccine dose ≤ 1.5 .

- To demonstrate the non-inferiority of RSVPreF3 OA investigational vaccine when co-administered with the PCV20 vaccine compared to RSVPreF3 OA investigational vaccine administered alone in terms of RSV-B neutralization antibody GMT ratio at 1 month after the RSVPreF3 OA investigational vaccine dose (i.e., at Day 31 [Visit 2] for the Co-Ad group and at Day 61 [Visit 3] for the Control group).

Null hypothesis vs. Alternative hypothesis:

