2.4. Estimands

The primary and secondary estimands to support regulatory decisions are described in the following table:

	Study Intervention	Population	Variable (or endpoint)	Intercurrent events (ICEs)		Population level summary
				Description	Handling strategy	
Primary	RSVPreF3 OA and PCV20 co-administered (Co-Ad) or received separately (Control)	Adults aged \geq 60 years of age (YOA)	Geometric Mean Titers (GMTs) for opsonophagocytic (OP) antibodies (Ab) titers for each of the pneumococcal vaccine serotypes (STs)	
 1. Permanently discontinued from study due to any reasons prior to Visit 2 blood sampling 2. Study intervention not administered per protocol 3. Prohibited medication or intercurrent medical condition prior to Visit 2 blood sampling 4. Vaccine or blood sample taken out of window 5. No pre/ post-vaccine immunogenicity result available 	
 1. Missing data won't be imputed. Summaries will present the actual data. 2. Participant excluded from the immunogenicity analysis. 3. Participant excluded from the immunogenicity analysis. 4. Participant excluded from the immunogenicity analysis. 5. Participant excluded from the immunogenicity analysis. 	Between group 2-sided 95% CI for the group GMT ratio in terms of OP antibody titers for each of the pneumococcal vaccine STs for PCV20 vaccine administered alone (Control) over PCV20 vaccine co-administered with RSVPreF3 investigational vaccine (Co-Ad group) at 1 month after the PCV20 vaccine (at Visit 2 for both groups).
Primary	RSVPreF3 OA and PCV20 co-administered (Co-Ad) or received separately (Control)	Adults aged \geq 60 YOA	GMTs for RSV-A neutralizing Ab titers	
 1. Permanently discontinued from study due to any reasons within 30 days of vaccine administration (Visit 2 for Co-Ad group; Visit 3 for Control group) 2. Study intervention not administered per protocol 	
 1. Missing data won't be imputed. Summaries will present the actual data. 2. Participant excluded from the immunogenicity analysis. 3. Participant excluded from the immunogenicity analysis. 	Between group 2-sided 95% CI for the group GMT ratio in terms of RSV-A neutralizing Ab titers for RSVPreF3 investigational vaccine administered alone (Control) over RSVPreF3 investigational vaccine co-

CCI [REDACTED]

PPD [REDACTED]

CCI [REDACTED]

[REDACTED]

[REDACTED]

[REDACTED]

[REDACTED]

[REDACTED]

[REDACTED]

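### SAP 5.5 gives two cut-offs for eliminating Control participants from the PCV per-protocol set: the post-RSV sample (Day 61) and Visits 1 and 2 (Day 31)

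*SAP*

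**What the plan says.** SAP 5.5 defines separate per-protocol sets for RSV and PCV. The last PCV PPS bullet runs the elimination criteria "up to blood sample post RSV vaccination for control group and Co-Ad group (i.e., control group and Co-Ad group participants need to meet" the criteria at stated visits. The bracket names those visits: "control group and Co-Ad group participants need to meet all above criteria at Visits 1 and 2".

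The corresponding RSV PPS bullet has the same main clause but explains it differently for Control: "control group participants need to meet all above criteria at Visits 2 and 3".

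The other PCV20 text points to Day 31:

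- The preceding PCV PPS bullet limits intercurrent conditions and prohibited medication or vaccination to the period "up to blood sample post PCV20 vaccination for control group and Co-Ad group, and".
- The PCV20 hypothesis in SAP 2.3 is evaluated "at 1 month after the PCV20 vaccine (i.e., at Day 31 [Visit 2] for both study intervention groups".
- The PCV estimand in SAP 2.4 lists as an intercurrent event "Prohibited medication or intercurrent medical condition prior to Visit 2 blood sampling".

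The SAP 5.5 footnote on intercurrent medical conditions gives the PCV20 interval as "Day 31 for Co-Ad group for PCV20 intervention" and names Control only with Day 61, for RSVPreF3 OA.

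**The concern.** An exclusion rule for a per-protocol set should stop when the outcome is measured. For PCV20 that is the Day 31 sample in both groups. The main clause goes further in Control, because RSVPreF3 OA is given there at Visit 2 and the post-RSV sample is drawn at Visit 3.

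Protocol 9.3.1 bases the confirmatory non-inferiority analyses on the PPS, and all 20 serotypes must pass, together with RSV-A, before RSV-B is tested. Under the literal clause, a Control participant with a valid Day 31 OPA result could be removed for something that happened later. No Co-Ad participant could be removed in that way.

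The documents supply a case. Protocol 5.2.2 covers vaccines not foreseen by the protocol up to 30 days after the last study dose, and Protocol 9.2.1 lists Section 5.2.2 among the possible grounds for elimination. A Control participant given such a vaccine between Visits 2 and 3 meets the criterion before the post-RSV sample but after the PCV20 outcome. The main clause counts this against the PCV PPS. The bracket and the preceding bullet do not.

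**Working it through.** **1. Dates, from the Protocol 1.3 schedule and Tables 3 and 4**

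| | Control | Co-Ad |
|---|---|---|
| Post-PCV20 sample | Visit 2, 30–42 days after Visit 1 | Visit 2, 30–42 days after Visit 1 |
| Post-RSV sample | Visit 3, 30–42 days after Visit 2 (60–84 days after Visit 1) | same Visit 2 sample |
| Extra elimination time under the main clause | 30–42 days | 0 |

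For Control the schedule footnote is explicit: "Sample collected at Day 61 will be used for the post-vaccination RSV vaccine-related testing".

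**2. Clause against bracket, Control**

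- PCV PPS main clause: ends at Visit 3 (Day 61).
- PCV PPS bracket: ends at Visit 2 (Day 31).
- RSV PPS, same main clause: its bracket ends at Visit 3, which fits.

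The same words are thus explained as Day 61 in one set and Day 31 in the other. Only the first matches the schedule.

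**3. The plan's power figure**

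Inputs from SAP 2.5: 490 evaluable per group, true ratio 1.05, margin 2, the 20 tabulated SDs, one-sided alpha 2.5%. For each serotype the type II error comes from the noncentral t distribution with

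- noncentrality = log10(2/1.05) / [SD × √(1/n_Control + 1/n_CoAd)],
- df = n_Control + n_CoAd − 2.

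Global power is 100% minus the sum of the 20 errors, as in the plan. At 490/490 the sum is 6.10% and power is 93.9% (plan: ~6.2% and ~93.8%). For 23F the error is 2.10%, as tabulated. The plan's figures reproduce.

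**4. Power if the literal clause removed Control participants**

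The documents give no rate for such events, so the losses are assumptions.

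| Assumed Control loss | n Control / n Co-Ad | Global PCV power |
|---|---|---|
| 0% | 490/490 | 93.9% |
| 1% | 485/490 | 93.7% |
| 5% | 465/490 | 92.9% |
| 10% | 441/490 | 91.7% |

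**5. Could selective removal change the conclusion?**

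Take the most variable serotype, 23F (SD 1.096), with an observed ratio of 1.05.

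- Half-width at 490/490: 1.96 × 1.096 × √(2/490) = 0.137 log10. Upper limit: 1.05 × 10^0.137 = 1.44.
- With 465 in Control: half-width 1.96 × 1.096 × √(1/490 + 1/465) = 0.139. Room to the margin: log10(2/1.05) − 0.139 = 0.280 − 0.139 = 0.141 log10.
- Removing a fraction f whose mean log10 titer differs by D from those who remain shifts the Control mean by f × D. At f = 0.05, reaching the margin needs D = 0.141/0.05 ≈ 2.8 log10, with the removed participants lower.

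**6. When the supporting ES analysis starts**

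SAP 15 adds an analysis on the Exposed Set when 5% or more of vaccinated participants with serology in any group are excluded from the PPS. With 490 Control participants in the PPS and x excluded, x/(490 + x) ≥ 5% first holds at x = 26 (26/516 = 5.04%; 25/515 = 4.85%). The plan allows for 545 − 490 = 55 non-evaluable per group, for all reasons.

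**The case against.** The strongest reply is that the SAP already resolves the reading. The bracket is the bullet's own explanation, and the preceding bullet, the hypothesis and the estimand all say Day 31. The first PCV PPS bullet asks only for PCV20 in Control, so someone who never received RSVPreF3 OA can be in the set but has no post-RSV sample. For that person only the bracket can be applied. The non-study vaccine example also falls in a category that the preceding bullet already cuts off at the post-PCV20 sample.

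Elimination is permissive in Protocol 9.2.1. SAP 5.1 leaves the detail of which deviations exclude a participant to a separate deviations management plan, which is not among these documents, with a review meeting and sponsor authorization before database lock. An event after the Day 31 draw cannot alter the Day 31 titer.

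Most of this stands as evidence that Day 31 was intended and that the practical effect is small. It does not make the clause correct. The PPS bullets are cumulative, so an earlier cut-off in one does not switch off a later cut-off in another. SAP 5.1 also has participants assigned under the SAP definitions and the final sets derived after lock, when a programmer must code one date. Later events cannot change a titer already measured, but they can change whose titers are analyzed.

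**Conclusion.** The contradiction is real and confined to Control. The main clause is wrong for a Day 31 outcome, and the weight of the text supports Visits 1 and 2. It should be corrected, because it is an operative rule for a confirmatory analysis set and, taken literally, excludes after the outcome in one arm only.

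The size is small. No planned sample size or power figure changes. The number of participants affected cannot be derived from the documents, and an actual exclusion is possible but not shown. Even an assumed 5% loss in Control costs about one percentage point of global PCV power. Under the planning assumptions for 23F, the participants removed would have to be about 2.8 log10 lower than those kept to bring the upper limit to 2. The conditional ES analysis is a further safeguard. These figures rest on the plan's SDs, a ratio of 1.05 and the assumed losses.

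The footnote is a lesser gap. Its list omits Control for PCV20, but its general sentence, read with the visit schedule, still gives Day 31.

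**What to change.** In the last PCV PPS bullet of SAP 5.5, change the reference from the post-RSV sample to the post-PCV20 sample (Visit 2) for both groups, so that clause, bracket, preceding bullet and estimand agree. In the footnote, add the Control group to the Day 31 interval for PCV20. Leave the RSV PPS bullet as it is.

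The cost is two phrases in the SAP and a check of one programming condition before the analysis sets are authorized. It needs no new data and no change to sample size or power.

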6. GENERAL CONSIDERATIONS

Data will be summarized descriptively (frequency and percentage for categorical data and mean, standard deviation [SD] and range for continuous data, unless specified otherwise). In summary tables for categorical data for which categories are defined on the eCRF, all categories will be presented as specified, even if the participants count within that category is zero.

Unless otherwise specified, all data collected during the trial will be presented in listings for the ENR.

6.1. Reference Start Date and Study Day

Study Day will be calculated from the reference start date and will be used to show start / stop day of assessments and events. It will appear in every listing where an assessment date or event date appears.

Reference start date is defined as Day 1 for the day of each vaccination, where study day is the number of days following the latest vaccination.

- If the date of the event is on or after the reference date, then:
$$\text{Study Day} = (\text{date of event} - \text{reference date}) + 1.$$
- If the date of the event is prior to the reference date, then:
$$\text{Study Day} = (\text{date of event} - \text{reference date}).$$

In the situation where the event date is partial or missing, Study Day, and any corresponding durations will appear partial or missing in the listings unless otherwise stated.

6.2. Baseline

Unless otherwise specified, baseline is defined as the last non-missing measurement taken prior to reference start date (including unscheduled assessments) and will be referenced as pre-vaccination. In the case where the last non-missing measurement and the reference start date coincide, and time is not collected, that measurement will be considered pre-vaccination. If time is not collected, Day 1 assessments are assumed to be taken prior to first dose and used as pre-vaccination values.

6.3. Retests, Unscheduled Visits and Early Termination Data

In general, for by-visit summaries, data recorded at the nominal visit will be presented.

Figure 1 is a bar chart comparing the number of patients with CCI (red bars) and PPD (blue bars) across six age groups. The x-axis represents age groups: 18-24, 25-34, 35-44, 45-54, 55-64, and 65 and older. The y-axis represents the number of patients, ranging from 0 to 100. CCI values are approximately 85, 75, 65, 55, 45, and 35 for each age group respectively. PPD values are approximately 25, 35, 45, 55, 65, and 75 for each age group respectively.

Age Group	CCI	PPD
18-24	85	25
25-34	75	35
35-44	65	45
45-54	55	55
55-64	45	65
65 and older	35	75

Listings will include scheduled, unscheduled, retest and early discontinuation data.

6.4. Windowing Conventions

Allowed time window for each visit will be performed as mentioned in “Schedule of Activities”, section 1.3 of protocol. Intervals between study visits are included in Table C: (Co-Ad group) and Table D (Control group).

Table C: Intervals between Study Visits (Co-Ad Group)

Interval	Planned visit interval	Allowed interval (Visit window)
Visit 1 (Day 1 / study intervention administration) → Visit 2 (Day 31)	30 days	30-42 days
Visit 1 → phone contact	180 days	180-210 days

Table D: Intervals between Study Visits (Control Group)

Interval	Planned visit interval	Allowed interval (Visit window)
Visit 1 (Day 1 / study intervention administration) → Visit 2 (Day 31)	30 days	30-42 days
Visit 2 (Day 31 / study intervention administration) → Visit 3 (Day 61)	30 days	30-42 days
Visit 2 → phone contact	180 days	180-210 days

